 The following intercurrent events are relevant to the estimand: Maternal death Terminal fetus/infant event (for newborn physical exam outcome measures) These intercurrent events will be addressed using a principal stratum approach. 	Infants born to women who discontinued follow-up before delivery or did not have available information will not be included (i.e., missing observations that would be relevant to the variable are considered missing completely at random). Given the descriptive nature of the primary analyses, there are no planned supplementary or sensitivity analyses. NOTE: The trial is designed to limit the frequency of missing data. For all women, clinical and laboratory evaluations will be abstracted from medical records and/or remote contact or telemedicine visits.
Population-level summary measure	Analysis approach
Mean weight, length, and head circumference from newborn physical exam for live infants born to women who received any amount of RDV for the treatment of COVID-19 while hospitalized	Mean of weight, length, and head circumference from newborn physical exam, bounded by a 95% CI calculated using the t distribution

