4.1 Inclusion Criteria – Arm 1 (Pregnant Women)

Women must meet all of the following inclusion criteria to be enrolled in Arm 1.

4.1.1 Of legal age or otherwise able to provide independent informed consent as determined by site SOPs and consistent with all applicable IRB policies and procedures, and is willing and able to provide informed consent for her own participation in this study.

Or

Of legal age to provide independent informed consent but is unable to provide informed consent (e.g. impaired capacity, as determined by site SOPs and consistent with all applicable IRB policies and procedures) and a Legally Authorized Representative (LAR) is willing and able to provide written informed consent on behalf of the participant in accordance with 21 CFR 50.27.

Note: All sites must follow the policies and procedures of all applicable IRBs; this includes single IRB (sIRB) policies and procedures. Refer to Section 13.1 for more information on sIRB oversight.

- **4.1.2** At study entry, viable intra-uterine pregnancy of any gestational age, based on medical records.
- **4.1.3** At study entry, hospitalized AND has confirmed or suspected COVID-19, based on medical records.
- **4.1.4** At study entry, receiving or expected to receive RDV for COVID-19 clinical care, as prescribed by the clinical care provider and documented in medical records.

Note: The study investigator or designee will confirm that a potential study participant is receiving or expected to receive RDV based on information in the medical record.

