Pregnancy/ Birth Outcomes	 Pregnancy outcome (outcome of pregnancy, congenital anomalies, date of outcome, narrative) Birth outcome (outcome location, type of delivery, infant date of birth, infant time of birth, infant gestational age, intrauterine growth classification, infant birth weight, infant biological sex at birth, Apgar scores, infant head circumference).

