9.6 Analyses

This section provides a brief summary of the planned statistical analyses. Details will be specified in a separate, comprehensive SAP. Section 10.4 describes the pharmacology data analyses and modelling, including the non-compartmental and population PK analyses.

The data analyses to address the primary and secondary PK and safety objectives will include descriptive statistics. PK outcome measures will be summarized using geometric means, arithmetic means, % CVs, and 90% CIs. The 90% CI for the arithmetic mean will be calculated on the log scale using the modified Cox approach(24). Continuous safety outcome measures, such as newborn birth weight, will be summarized using mean and median as measures of location and the standard deviation and quantiles of minimum, 25th percentile, 75th percentile, and maximum as measures of dispersion. Categorical safety outcome measures will be summarized using proportions and exact binomial (Clopper-Pearson) 95% CIs. Descriptive statistics will also be presented by trimester for Arm 1

For the objectives that compare PK parameters between arms, 90% CIs for the geometric mean ratio (GMR) of the PK parameters in study pregnant women versus non-pregnant women will be calculated to assess whether or not there is a greater than 30% difference in exposure in pregnant women versus non-pregnant women. The confidence coefficient will be 90% rather than 95% to match the usual practice in the PK literature. We will use Schuirmann's two one-sided tests (TOST) approach to show that the means of the two groups do not differ by more than the 30% margin of equivalence, i.e.: the 90% CI of the GMR is between 0.7 and 1.43(26). As discussed in Section 9.1, the 30% margin is a preliminary analysis approach (due to paucity of available data), and the SAP will be updated to include additional analyses to assess adequacy of dosing during pregnancy as more information on the PK and pharmacodynamics of RDV in adults with COVID-19 becomes available.

For women who deliver within 5 days after receiving RDV, placental transfer will be assessed by comparing the drug concentrations of RDV and GS-441524 in plasma from cord blood with concentrations in maternal plasma at delivery using the GMR with a 90% CI.

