2.5 Formal Interim Monitoring

No formal interim analyses were planned or specified in the study protocol. The plans for study monitoring are described in Section 9.5 of the protocol (Version 2.0).

3 Outcome Measures

3.1 **Primary Outcome Measures (Arm 1)**

- 1. [For Primary Objective 1] Non-compartmental PK parameters:
 - a. RDV area under the plasma concentration-time curve (AUC)
 - b. RDV half-life (t_{1/2})
 - c. GS-441524 trough concentration (Ctrough)
- 2. [For Primary Objective 2] Clinical and laboratory safety outcomes:
 - a. Maternal renal adverse events of any grade through 7 days post-last infusion
 - b. Maternal hepatic adverse events of any grade through 7 days post-last infusion
 - c. Maternal hematologic events of any grade through 7 days post-last infusion
 - d. Adverse events through 4 weeks post-last infusion and during delivery:
 - i. Maternal Grade 3 or higher adverse events
 - ii. Serious adverse events
 - iii. Maternal Grade 3 or higher adverse events assessed as related to RDV by the CMC
 - e. Labor/delivery outcomes:
 - i. Pregnancy loss
 - ii. Congenital anomalies
 - iii. Preterm birth (< 37 weeks, < 34 weeks)
 - iv. Small for gestational age (SGA) (< 10th percentile for gestational age)
 - f. Newborn physical exam:
 - i. Birth weight
 - ii. Length
 - iii. Head circumference

Note: Additional non-compartmental PK parameters, described in Table 2 of the PK SAP, will also be summarized for Arm 1 as part of the Primary Analysis Report for RDV, GS-441524, and/or GS-704277 (data permitting).

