Continuous variables will be summarized by N, N missing, mean, standard deviation, and quantiles of minimum, 25th percentile, median, 75th percentile, and maximum. Categorical variables will be summarized by N (%) in each category, excluding the missing category in the denominator. PK parameters will be also summarized using geometric and arithmetic means, % CVs, and 90% CIs. The 90% CI for the arithmetic mean will be calculated on the log scale using the modified Cox approach (Olsson, 2017). The 90% CI for the geometric mean will be calculated using the t distribution on the log scale.

The Pre-infusion Period will refer to the period 48 hours before initiation of RDV infusions for COVID-19. If there is more than one record before the start of infusions, the last one before it (proximal) will be used, unless otherwise noted. The Infusion Period begins at the start of the first infusion and continues through the day of the last infusion, and the Safety Follow-up Period begins from the first day after the last RDV infusion and continues for 4-weeks after the last RDV infusion. This period is divided into 3 data collection time points: 48-Hours, 7-Days, and 4-Weeks

Post-Last Infusion. For Arm 1, the Delivery Period is defined as the period from onset of labor or start of Cesarean section through 24 hours after delivery.

Because women of any gestational age can be enrolled in the study and each trimester of pregnancy provides differing physiological changes that can affect bioavailability of drugs, primary analyses will also be presented by trimester for Arm 1.

5 Estimands and Estimation

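### Newborn weight, length and head circumference are summarised only on the raw scale; a supplementary gestational-age- and sex-specific z-score would make them interpretable

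*SAP*

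**What the plan says.** SAP 5.1.3 (Third Primary Estimand) takes as its variables birth weight in grams, and length and head circumference in centimetres, in live infants born to women who received any remdesivir. The analysis is "Mean of weight, length, and head circumference from newborn physical exam, bounded by a 95% CI calculated using the t distribution". On further analyses it states: "Given the descriptive nature of the primary analyses, there are no planned supplementary or sensitivity analyses".

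Other summaries of the same measures are planned:
- SAP Section 4: "Continuous variables will be summarized by N, N missing, mean, standard deviation, and quantiles of minimum, 25th percentile, median, 75th percentile, and maximum".
- Protocol 9.6: "Continuous safety outcome measures, such as newborn birth weight, will be summarized using mean and median as measures of location", with SD and quantiles for spread.
- SAP Section 4 also states that "primary analyses will also be presented by trimester for Arm 1".

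Under the same primary objective, SAP 3.1 lists preterm birth (below 37 and below 34 weeks) and "Small for gestational age (SGA) (< 10th percentile for gestational age") as separate outcomes. SAP 5.1.2 gives each an exact 95% CI.

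Entry to Arm 1 requires a "viable intra-uterine pregnancy of any gestational age, based on medical records" (Protocol 4.1.2). The birth outcomes in Protocol Table 6 include "infant gestational age, intrauterine growth classification, infant birth weight, infant biological sex at birth", Apgar scores and head circumference. Length is not in that list, although Protocol Table 7 and SAP 3.1 name it as a primary outcome.

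**The concern.** Size at birth depends strongly on gestational age at birth. The plan anticipates a mix of gestational ages, since preterm birth has two thresholds among the primary outcomes. Arm 2 has no newborns, so a reader can only set the Arm 1 means against an outside reference, and any useful reference for newborn size is specific to gestational age and sex.

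A low mean weight or head circumference could therefore come from early delivery with normal growth, from poor growth at term, or from both. The SAP accepts for weight that size should be judged against gestational age, because that is how it defines SGA. It does not carry this over to length or head circumference, or to weight as a continuous measure.

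Presentation by trimester does not solve this. SAP Section 4 justifies it by physiological changes that affect drug bioavailability, and does not tie it to gestational age at birth. A woman enrolled late in pregnancy cannot have a very early birth, whereas one enrolled in the second trimester can. Raw newborn means by trimester would then compare groups with different gestational-age mixes.

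**Working it through.** **The plan's own figures.** Neither document states an SD, precision or effect size for newborn measurements. The nearest stated safety figure is the exact 95% CI for 4/20 in SAP Table 2, printed as 6% to 44%. Clopper-Pearson gives 5.7% to 43.7%, which agrees.

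**Step 1. Which measures have a gestational-age-standardised summary?**

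| Measure | Raw-scale summary | Standardised for gestational age |
|---|---|---|
| Birth weight | mean, 95% t-interval, SD, quantiles | SGA, yes/no only |
| Length | same | none specified |
| Head circumference | same | none specified |

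**Step 2. How far can early delivery alone move the raw mean?** All growth inputs here are assumptions: 3450 g at 40 weeks, 190 g per week (range 150 to 230), SD 420 g at fixed gestational age, term births uniform over 37–41 weeks (mean 39), preterm births uniform over 30–37 weeks (mean 33.5), 20 live infants, and no growth effect.

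- 10% preterm: mean gestational age 0.9×39 + 0.1×33.5 = 38.45 weeks. Mean weight 3450 − 190×1.55 = 3155.5 g.
- 30% preterm: mean gestational age 0.7×39 + 0.3×33.5 = 37.35 weeks. Mean weight 3450 − 190×2.65 = 2946.5 g.
- Fall: 190×1.10 = 209 g. At 150 and 230 g per week it is 165 g and 253 g.

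**Step 3. Interval width at 30% preterm.**

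- Variance of gestational age: 0.7×16/12 + 0.3×49/12 + 0.3×0.7×5.5² = 8.51 weeks².
- Raw SD of weight: √(190²×8.51 + 420²) ≈ 695 g.
- Half-width factor at n = 20: 2.093/√20 = 0.468.
- Raw half-width: 0.468×695 ≈ 325 g (284 to 370 g over the slope range).
- Standardised scale: 0.468×420 ≈ 197 g-equivalent. This figure is proportional to the assumed SD of 420 g.

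A simulation of 40,000 trials gives average half-widths of 321 g and 194 g. These are slightly smaller because the sample SD averages a little below the true SD at n = 20.

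**Step 4. Do the planned outcomes separate the two explanations for weight?** In SD units, if a share q of infants is preterm but normally grown, with a raw deficit of d SD, the mean falls by q×d. With q = 0.3 and d = 2 the fall is 0.6 SD, the same as a uniform 0.6 SD growth deficit at term. The planned proportions would be about:

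| Scenario, n = 20 | Preterm (95% CI) | SGA (95% CI) |
|---|---|---|
| Early delivery, normal growth | 6/20 (12–54%) | 2/20 (1–32%) |
| Term delivery, 0.6 SD growth deficit | 0/20 (0–17%) | 5/20 (9–49%) |

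The pattern differs, so SGA and preterm birth do carry information. The SGA intervals overlap heavily.

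**Step 5. What does the SGA dichotomy lose?** Under a uniform deficit of δ SD, the probability of SGA is Φ(−1.2816 + δ). At n = 20 the exact CI excludes 10% only with 6 or more SGA infants (lower limit 8.7% at 5/20, 11.9% at 6/20). For the z-score, the chance that the 95% t-interval excludes 0 comes from the noncentral t distribution.

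| δ (SD) | P(SGA) | SGA CI excludes 10% | z-score CI excludes 0 |
|---|---|---|---|
| 0.5 | 0.217 | 26% | 56% |
| 0.6 | 0.248 | 37% | 72% |

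No test is planned. These percentages only compare how much information the two summaries carry.

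**The case against.** The strongest reply is that the raw mean is a valid estimate of the estimand the SAP states: mean size of live infants born to treated women. The study is descriptive, with no hypothesis (SAP 2.2). Gestational age at birth follows exposure and is part of a primary outcome, so standardising by it removes any effect on size that acts through early delivery. An interval that carries the gestational-age spread is correct for the stated estimand. Weight, length and head circumference are also the outcomes listed in Protocol Table 7. All of this stands, and it is why z-scores should be added and should not replace the raw means.

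Three stronger readings are tempting, and the documents do not support them:
- *Early delivery and poor growth cannot be told apart.* Preterm birth and SGA are separate primary outcomes, and Step 4 shows that they point in different directions. For weight the separation is partial, not absent.
- *The means are confounded.* There is no newborn comparison to confound. The accurate statement is that the means are hard to interpret without gestational age.
- *Only means are planned.* SD, median, quantiles and a by-trimester presentation are also planned, though all on the raw scale.

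Table detail sits in the Analysis Implementation Plan, which is not among the documents. A display of newborn size beside gestational age there cannot be ruled out. The SAP nevertheless fixes the estimand and says that no supplementary analysis is planned for it.

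The gram figures rest wholly on assumed inputs. The 209 g fall is smaller than the raw half-width at 30% preterm, and the tripling of the preterm share behind it would be visible in the preterm outcome.

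**Conclusion.** The point holds as an improvement to interpretability, not as an error in estimation. SAP 5.1.3 leaves three primary newborn outcomes on a scale that cannot be interpreted without gestational age at birth. For weight, the gap is the loss of information from relying on a yes/no SGA outcome at about 20 infants. For length and head circumference, neither document specifies any standardised measure.

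The size is illustrative. A shift of about 209 g (165 to 253 g) in mean birth weight can arise with no growth effect, and the raw half-width at 30% preterm is roughly 325 g against 197 g-equivalent when standardised. Both depend on the assumed slope, SD and gestational-age spread. The absence of a standardised length or head-circumference summary does not depend on those assumptions.

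**What to change.** Keep the raw means with their t-intervals as the protocol-listed outcome, and add to SAP 5.1.3 one supplementary summary, overall and by trimester:

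- Mean gestational-age- and sex-specific z-score, with 95% t-interval, for birth weight, head circumference and, where captured, length.
- Gestational age at birth shown beside both the raw and the standardised summaries.
- One named growth reference, which for weight is the one used to classify SGA.
- The number of infants outside the reference range.

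Infant gestational age and sex are already in Protocol Table 6, so weight and head circumference need only SAP wording and a few lines of code. There are three costs. A reference must be chosen. Infants outside its gestational-age range would appear only in the raw summary. And because Table 6 does not list length, its capture must be confirmed for the planned raw mean as well as for the z-score.

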5.2 Secondary Estimands

5.2.1 First Secondary Estimand

Secondary Objective 1: To describe the pharmacokinetics of RDV and its metabolite, GS-441524, after administration to non-pregnant women of childbearing potential as part of clinical care			
Estimand description	Geometric mean of PK parameter (RDV AUC/RDV t _{1/2} / GS-441524 C _{trough}) in hospitalized non-pregnant woman of childbearing potential, who tolerated at least 3 RDV infusions for the treatment of COVID-19.		
Treatment	Remdesivir (RDV)		
Target population	ו	Analysis set	
Hospitalized non-pregnant women of childbearing potential who received and tolerated at least 3 RDV infusions for the treatment of COVID-19		PK-evaluable women (PK Evaluable analysis set) NOTE: Women will be considered PK evaluable if they have at least 3 out of 4 of	

	the pre-dose through 3 hours post-end-of- infusion (post-EOI) intensive PK samples, either the 5 hours post-EOI or the 7 hours post-EOI intensive PK sample, and either the pre-dose or 23 hour post-EOI samples collected. In addition to these minimum requirements for sample collections, drug concentrations will also be reviewed once available to further assess whether the participant is PK evaluable. For t _{1/2} , women will be PK evaluable if they have the additional requirement of 3 consecutive declining points in the curve.
Variable(s)	Outcome measure(s)
 RDV concentration in plasma RDV concentration in plasma GS-441524 concentration in plasma 	 Non-compartmental PK parameters: 1. RDV area under the plasma concentration-time curve (AUC) 2. RDV half-life (t_{1/2}) 3. GS-441524 trough concentration (C_{trough})
Handling of intercurrent events	Handling of missing data
 The following intercurrent events are relevant to the estimand: 1. Discontinue treatment for toxicity or non-toxicity reasons 2. Death 	Only participants who are deemed PK evaluable will be included in the final analysis (i.e., missing observations due to missing or inadequate sampling are considered missing completely at random).
These intercurrent events will be addressed using a principal stratum approach.	Participants who do not undergo intensive PK sampling will not be included in the final analysis (i.e., missing observations due to drop out prior to intensive PK sampling are considered missing completely at random).
	Given the descriptive nature of the primary analyses, there are no planned supplementary or sensitivity analyses.
Population-level summary measure	Analysis approach
Geometric mean of PK parameter (RDV AUC/RDV T1/2/ GS-441524 C _{trough}) in	Geometric mean of PK parameter (RDV AUC/RDV T1/2/ GS-441524 C _{trough}),
hospitalized non-pregnant women of	bounded by a 90% CI calculated using the t
childbearing potential	distribution on the log scale

5.2.2 Second Secondary Estimand

Secondary Objective 2: To describe the clinical and laboratory safety outcomes through 4 weeks post-infusion in non-pregnant women of childbearing potential receiving RDV as part of clinical care.		
Estimand description	(A) Probability of a non-pregnant woman of childbearing potential, who received any amount of RDV while hospitalized for the treatment of COVID-19,* having at least one adverse event (renal/hepatic/hematologic of any grade) or death through 7 days post last infusion.	
	(B) Probability of a non-pregnant women of childbearing potential, who received any amount of RDV while hospitalized for the treatment of	

Treatment	 COVID-19,* having at least one adverse event (Grade 3 or higher/serious/Grade 3 or higher assessed as related by the CMC) or death through 4 weeks post last infusion and at delivery. *NOTE: This study design is opportunistic in that it enrolls women who may have already received at least one infusion of RDV. Because participants can be enrolled any time prior to the 4th infusion, the study population will potentially not include women who started RDV and discontinued it prior to the 4th infusion due to toxicity, intolerance, virologic failure, or any other reason. Consequently, the results may be overly optimistic. Remdesivir (RDV) 		
Target population		Analysis set	
Non-pregnant women of childbearing potential who received any amount of RDV while hospitalized for treatment of COVID-19* *NOTE: This study design is opportunistic in that it enrolls women who may have already received at least one infusion of RDV. Because participants can be enrolled any time prior to the 4 th infusion, the study population will potentially not include women who started RDV and discontinued it prior to the 4 th infusion due to toxicity, intolerance, virologic failure, or any other reason. Consequently, the results may be overly optimistic.		Non-pregnant women who received any amount of RDV (Safety analysis set)	
Variable(s)		Outcome measure(s)	
 (A) Occurrence of each of the following through 7 days post-last infusion: 1. Renal adverse events of any grade 2. Hepatic adverse events of any grade 3. Hematologic adverse events of any grade 		Outcome measures as defined by the variables	
through 4 weeks 1. Grade 3 2. Serious a 3. Grade 3 assessed CMC	f each of the following post-last infusion: or higher adverse events adverse events or higher adverse events d as related to RDV by the		
Handling of interc		Handling of missing data	
the estimand: 1. Death This intercurrent a composite ever A supplementary principal stratum	ercurrent event is relevant to event will be addressed using at approach. analysis that applies a approach for maternal death elevant outcome measures.	Missing data will be handled using an "available case" approach. Outcome measures for participants who discontinue follow-up before the time point of interest (i.e., 7 days post-last infusion/4 weeks post- last infusion) and did not have an event of interest will be missing (i.e., these participants will not be included in the denominator).	

	As a sensitivity analysis, we will use multiple imputation over a range of potential probabilities, including "best case" (i.e., probability of event = 0) and "worst case" (i.e., probability of event = 1) scenarios.
Population-level summary measure	Analysis approach
(A) Probability of a non-pregnant women of childbearing potential, who received any amount of RDV for the treatment of COVID-19, having at least one adverse event (renal/hepatic/hematologic of any grade) through 7 days post last infusion	 (A) Proportion of participants with at least one adverse event (renal/hepatic/hematologic of any grade) through 7 days post last infusion, bounded by an exact 95% Cl (B) Proportion of participants with at least one adverse event (Grade 3 or higher/serious/
(B) Probability of a non-pregnant women of childbearing potential, who received any amount of RDV for the treatment of COVID-19, having at least one adverse event (Grade 3 or higher/serious/ Grade 3 or higher assessed as related by the CMC) through 4 weeks post last infusion	Grade 3 or higher assessed as related by the CMC) through 4 weeks post last infusion, bounded by an exact 95% Cl

6 Report Contents

This section lists the major report contents for the Primary Analysis Report. Detailed descriptions of the content of each of the following sections are given in the AIP.

- 1 Introduction
- 2 Background
 - I. Study Design
 - II. Objectives
 - III. Outcome Measures
- **3** Study History and Monitoring History
- 4 Statistical Considerations
 - I. General Considerations
 - II. Estimands and Estimation
- 5 Disposition
 - I. CONSORT Diagram
 - II. Accrual
 - III. Evaluability
- 6 Baseline Characteristics
- 7 Study Status and Retention
- 8 Status of Drug under Study and Hospitalization
- 9 Primary Analyses [Arm 1]
 - I. Non-compartmental PK Outcome Measures
